2 PROJECT OBJECTIVES AND DESIGN

2.1 Objectives and Hypothesis

- i) To determine the extent of infection in the special population of police officers of the canton Bern. We hypothesize that the COVID-19 seroprevalence within the police department will be between 1% and 2% at the beginning of the study. We further hypothesize that the seroprevalence will increase during the study period by 8% (i.e., from 2% to 10%). The rationale for this increase proportion derives from the Geneva study, and the ongoing COVID-19 pandemic till the end of study period [11].
- ii) To determine risk factors for infection by comparing the proportion of seropositivity (infected versus noninfected individuals). We hypothesize that police officers with fieldwork activity will have a higher seroprevalence than will office and administration personnel. We hypothesize that working in the city of Bern will be associated with a higher seroprevalence than will working in other geographic areas of the canton (i.e. rural area).
- iii) To monitor COVID-19 antibody titres and neutralizing capacity over time and to associate them with reinfection rates and infection-free intervals in police officers after accidental contact with a proven COVID-19 case. We hypothesize that in seropositive individuals, there will be a decreasing dynamic of antibody titres over the one-year study period, and hence, a decrease of neutralizing capacity.

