2.2 Primary and secondary endpoints

Primary endpoint: The variable of primary interest is **COVID-19 seropositivity**. This variable is measured at five time points over the one-year study period. The following baseline factors may have an influence on the primary endpoint and will be obtained: (i) pre-existing comorbidities, (ii) rural versus city distribution of working place, and (iii) office work versus field work.

Secondary endpoints: We will assess the proportion of symptomatic and asymptomatic cases among seropositive participants. We will calculate the attack rate in different subgroup. These include (i) study participants with health-related risk factors (age>50 and age>60 years, diabetes, arterial hypertension, cardiovascular disease, chronic pulmonary disease, immune-compromised status due to host diseases, medical treatment, cancer, obesity), (ii) activity-related subgroups (i.e. fieldwork vs office activity), (iii) geography-related subgroups (i.e. city vs rural areas). In follow-up visits, the antibody titers (i.e. dynamic) and the neutralization capacity will be assessed. Thereby we will determine the change in serum levels of SARS-CoV-2 antibodies over time in seropositive participants.

2.3 Project design:

This is a single center special population (i.e. police officers of the canton of Bern) seroprevalence survey. It is a repeated cross-sectional investigation in the canton of Bern combined with a longitudinal cohort study with serial sampling of the included study participants. The protocol is aligned with the one of seroprevalence studies recommend by the WHO [25].

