In serum samples with positive antibody test, quantification of neutralizing antibodies will be performed at the IFIG. They will be measured by pre-incubating serial dilutions of baseline and convalescent serum with 200 to 400 plaque forming units (PFU) of SARS-CoV-2, after which a PFU reduction assay will be performed on Vero-E6 cells. After 2 days, cells will be fixed and stained with crystal violet to analyse the neutralizing capacity of antibodies generated towards SARS-CoV-2, as previously described [26].

The results of Anti-SARS-CoV-2-Test of will be communicated to study participant via e-mail within 2 weeks of blood sampling. The results of neutralization capacity will be communicated at the end of the study period. This experimental assay will be performed in the research laboratory with all positive samples during one month, at the end of the study period.

Seropositive participants or participants with a positive SARS-CoV-2 test in the past (PCR or antigen test) will be asked to complete an additional questionnaire that investigates possible contacts (i.e., working versus private environment) and sources of transmission (see point 5 in the BASEC application: "CASE REPORT FORM").

Seropositive participants or vaccinated participants will be contacted by the study team within 4 weeks after laboratory result, for one additional blood sampling that investigates neutralization capacity. Seropositive participants with vaccination will be contacted twice. Figure 2 illustrates the sampling scheme.

Antibodies	Vaccine	No. of blood sampling in 1 year
		
negative	no	5 baseline + every 3 months
positive	no	6 baseline + every 3 months + 1 sampling
negative	yes	6 baseline + every 3 months + 1 sampling
positive	yes	7 baseline + every 3 months + 2 samplings

Figure 2: Schematic overview of the blood sampling over one year

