The duration of both antibody persistence and neutralizing capacity over time is unknown. Because we are generating a cohort, we are able to monitor antibody levels over 1 year. Similarly, we are able to investigate the neutralizing capacity in study participants who repeatedly test positive for SARS-CoV-2. These data are important to evaluate possible immunity over time, both after virus exposure and – if available – after vaccination.

The burden and time effort for participants is minimal. We are not using genetic data, nor are we investigating a vulnerable patient population. Therefore, we are convinced that there is an overall fair balance for the study participant.

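### Neutralisation is assayed only on samples that are themselves antibody-positive, so the decline in neutralising capacity under objective iii is likely to be understated, by an amount the documents do not fix

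*Combined protocol and SAP*

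**What the plan says.** Section 3.3 (Study procedures) gives the laboratory rule: "In serum samples with positive antibody test, quantification of neutralizing antibodies will be performed at the IFIG". A later paragraph repeats it, stating that the experimental assay is run "with all positive samples during one month, at the end of the study period". Both sentences select samples, not participants.

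The same section makes one exception. Seropositive or vaccinated participants are called back "for one additional blood sampling that investigates neutralization capacity", and Figure 2 includes an antibody-negative, vaccinated row with one such draw.

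Section 2.1, objective iii, hypothesises that in seropositive individuals "there will be a decreasing dynamic of antibody titres over the one-year study period, and hence, a decrease of neutralizing capacity". Section 2.2 lists the secondary endpoint without a sample-level limit: "In follow-up visits, the antibody titers (i.e. dynamic) and the neutralization capacity will be assessed". Section 6.1 says of the cohort that "we are able to investigate the neutralizing capacity in study participants who repeatedly test positive for SARS-CoV-2".

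Section 3.3 schedules five samplings whatever the serostatus and runs two binding assays, anti-nucleocapsid and anti-spike, on each sample. It does not say which assay defines a positive test. Section 4.1 names mixed models for antibody titres and no model for neutralisation. Section 4.2 uses all available data and relies on mixed models to deal with missing values.

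**The concern.** Take a participant who is antibody-positive at visits 1 to 3 and negative at visits 4 and 5. Under section 3.3 this person has three neutralisation results and then none. No section assays the two later sera or assigns them a value. Whether a neutralisation value exists therefore depends on the binding result at that same visit, and section 2.1 itself treats binding titre as the driver of neutralisation. Later visits would describe mainly those who kept their antibodies.

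At stake are the estimated rate at which neutralising capacity falls and the planned link between neutralising capacity and reinfection under objective iii. The matter is separate from vaccination: it arises in unvaccinated participants who simply wane.

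**Working it through.** **What the documents supply.** There is no sample size, slope, variance, seroreversion rate or binding-neutralisation correlation for this endpoint, so there is no figure to reproduce. The sizing table in section 4.1 concerns the width of seroprevalence intervals. Section 6.1 states that the persistence of antibodies and of neutralising capacity is unknown. What can be taken from the plan is:
- Five visits, three months apart (section 3.3).
- About 1,000 participants with seroprevalence rising from 2% to 10% (section 4.1): 0.02 × 1,000 = 20 seropositive at baseline and 0.10 × 1,000 = 100 at the end.

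**Why the mixed model does not settle it.** A mixed model on available data is valid if, given the values in the model, absence does not depend on the unseen value. Here absence depends on the same-visit binding titre. A model of neutralisation alone does not contain that titre, and the titre is correlated with the unseen neutralisation value.

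**Simulation.** For person i at visit t = 0 to 4, log2 neutralising titre = a_i + b_i·t + e_it, with binding titre built the same way. The correlation between the two is ρ at each level (intercept, slope, residual). Assumed inputs: mean slope −0.5 per visit, intercept SD 1.5, slope SD 0.25, residual SD 0.5. From 1,500 simulated people per scenario, those binding-positive at visit 1 were kept (1,399 to 1,499). The cut-off was set so that a given share of them were negative at visit 5. A random-intercept model was fitted to all samples and then to positive samples only. Understatement = 1 − (positive-only ÷ all), calculated before rounding.

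| Seroreverted by visit 5 | ρ | Slope, all samples | Slope, positive only | Slope too shallow by | Fall in visit means understated by |
|---|---|---|---|---|---|
| 5% | 0.5 | −0.493 | −0.486 | 1.3% | 4.5% |
| 5% | 0.9 | −0.493 | −0.480 | 2.6% | 9.1% |
| 10% | 0.5 | −0.493 | −0.482 | 2.2% | 7.3% |
| 10% | 0.9 | −0.493 | −0.467 | 5.3% | 16.7% |
| 20% | 0.5 | −0.494 | −0.469 | 5.1% | 14.3% |
| 20% | 0.9 | −0.494 | −0.446 | 9.8% | 28.8% |
| 40% | 0.5 | −0.496 | −0.442 | 10.7% | 25.3% |
| 40% | 0.9 | −0.495 | −0.395 | 20.3% | 50.0% |

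At ρ = 0 the slope differed by −1.5% to +0.1%, so there was no understatement. A separate run at ρ = 0.6 to 0.8 gave slopes too shallow by about 2%, 3-4%, 6-8% and 14-16% at the four seroreversion levels, within the ranges above.

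**Bias against precision.** With the same inputs and 20 people with complete data, the standard error of the mean slope is √((0.25² + 0.5²/10)/20) = √(0.0875/20) ≈ 0.066 log2 per visit. Here 10 is the sum of squared deviations of the five visit times. At 20% seroreversion (0.20 × 20 = 4 people) the bias is 0.494 − 0.469 = 0.025 to 0.494 − 0.446 = 0.048, below one standard error. At 40% it is 0.054 to 0.100, about 0.8 to 1.5 standard errors.

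**False positives.** At 2% prevalence, 980 of 1,000 are truly negative. The specificity of 99% in section 4.1 gives 980 × 0.01 ≈ 10 false positives per visit; the manufacturer's 99.81% in section 3.3 gives 980 × 0.0019 ≈ 2. The comparison is with about 20 true positives at baseline.

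**The case against.** The strongest reply is that little is lost. Sampling continues at all five visits, and both binding assays are run on every sample. A reader might infer that seroreverters drop out of follow-up, or that the whole of objective iii is biased. The documents do not support either: the binding-titre half of the objective is untouched by this rule. The continuing binding readings could also support a joint model of the two titres that would account for the selection under its own assumptions, but the plan does not specify one.

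A reader might also infer that neutralisation is never measured in an antibody-negative person, or that section 6.1 confirms a restriction to repeat positives. Figure 2 contradicts the first for vaccinated participants, though that is a single draw and gives an unvaccinated seroreverter nothing. The wording in section 6.1 says only what the cohort makes possible and does not specify antibody testing. Section 2.2 carries no sample-level limit, so the sections need reconciling, but the explicit laboratory instruction is the one in section 3.3.

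Three further points stand and lower the weight:
- If positivity on either assay counts, losing one antibody does not end neutralisation testing, and fewer values go missing.
- With about 20 baseline positives, the bias at moderate seroreversion is smaller than sampling error.
- The bias runs against the hypothesised decline, so a detected decline would be conservative. The estimated size of the decline would still be too small.

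It is tempting to add that the share retaining neutralisation would be overstated. That share is not an endpoint in section 2.2, so the point is not pressed.

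**Conclusion.** The point holds for the neutralisation part of objective iii. As written, section 3.3 selects neutralisation values on a marker of the outcome, and nothing elsewhere in the plan repairs this. The direction, too shallow a decline, follows if binding and neutralising titres are positively related, as section 2.1 presupposes.

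The size cannot be fixed from the documents. Under the assumed inputs and correlations of 0.5 to 0.9, the mixed-model slope is too shallow by roughly 1-5% at 5-10% seroreversion, 5-10% at 20% and 11-20% at 40%. Crude visit means are worse, at up to 50%. These figures depend on the assumed variances, slope and correlation, and on which assay defines a positive test. This is a secondary endpoint and the bias may be modest, but the correction is cheap and possible only while the serum exists.

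**What to change.** In section 3.3, replace both sample-level sentences ("In serum samples with positive antibody test, quantification of neutralizing antibodies will be performed at the IFIG" and "This experimental assay will be performed in the research laboratory with all positive samples during one month, at the end of the study period") with a participant-level rule: assay all scheduled samples, from the first positive one onward, of every participant whose seropositivity was confirmed by the repeat sampling described under the measures to reduce bias, whatever the later antibody result. Keep the vaccination-triggered samples. Limiting the rule to confirmed positives matters, because otherwise the 2 to 10 false positives expected per visit would add repeated below-limit values from people never infected.

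Also:
- State whether anti-nucleocapsid, anti-spike or either defines a positive test, and what repeat result counts as confirmation.
- In section 4.1, name the neutralisation model and enter values below the assay limit as left-censored, not missing. A joint model with binding titre would be a useful sensitivity analysis.
- Align section 6.1 ("investigate the neutralizing capacity in study participants who repeatedly test positive for SARS-CoV-2") with the new rule.

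The cost is small. If seropositives grew evenly (20, 40, 60, 80, 100 across the visits, an assumption), scheduled samples after the first positive would number 20×4 + 20×3 + 20×2 + 20×1 = 200. If 5% to 40% of these were negative, the addition is 10 to 80 assays, with no new visit or draw. They fit the single batch at study end, which must be run before samples without further-use consent are destroyed (section 7.4).

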Each sample will be labelled with the study participant's code immediately prior to blood withdrawal. For each serum sample collected, the time of collection, the conditions for transportation, and the time of arrival at the study laboratory will be recorded. Given the efficient means of transport in the canton of Bern, we anticipate that serum samples will reach the laboratory within the same day after collection. They will be aliquoted and stored at our at the Interregionale Blutspende SRK (-30°C), for coordinated analysis of batches. The diagnostic laboratories of both the Interregionale Blutspende SRK and the IFIG have the required government permits to operate a diagnostic service for clinical specimens of human origin, including storage of such specimens; furthermore, they are accredited to the ISO/IEC 17025 Standard.

On each sample two commercially available SARS-CoV-2 serological assays will be performed (Elecsys® Anti-SARS-CoV-2-Test). According to the manufacturer's information, the specificity is 99.81 % (95% CI 99.65 – 99.91 %) and sensitivity 100 % (88.1 – 100 %), respectively. The rationale for using this particular test includes a performance evaluation at the Interregionale Blutspende SRK that demonstrated a high specificity (Riester et al. medRxiv 2020.08.07.20169987). Overall specificities for the Elecsys Anti-SARS-CoV-2 immunoassay in 9575 samples from blood donors (n = 6714) and routine diagnostic testing specimens (n = 2861) were 99.82% (95% CI 99.69-99.91) and 99.93% (95% CI 99.75-99.99), respectively. In addition, the test will be purchased to a reasonable price. The rationale for choosing two commercially available SARS-CoV-2 serological assays is the following. One test detects anti-nucleocapsid antibodies, while the other detects anti-spikeprotein antibodies. Anti-nucleocapsid antibodies detect antibodies derived from natural infection but do not detect antibodies derived from mRNA-vaccination. It is important for both the investigator and the study participant to identify antibodies derived from vaccination. Therefore, we complement the tests for anti-nucleocapsid antibodies with tests for anti-spike-protein antibodies. Testing will be carried out at the Interregionale Blutspende SRK.

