Measures taken to reduce expected biases: If study participants reveal anti-SARS-CoV-2-antibodies at baseline or reveal seroconversion during the study year, additional investigations will be performed. Serum sampling will be repeated 2 and 4 weeks after the first positive antibody test result to confirm seropositivity and to exclude false positive results. It is possible that among the study participants, scientifically motivated persons or individuals keen to know their serostatus will in particular volunteer to donate samples. Such a scenario points towards a convenience sampling, and has a higher uncertainty bias in comparison to random samples. We will try to counterbalance this potential bias by including a large sample size (i.e., high proportion of the total number of employees) and by monitoring the age distribution during recruitment. Another potential bias includes the social pressure from superiors or peers to participate. We have included the following counter measures: First, there is no possibility for superiors to identify participating employees at the time of recruitment if study volunteers sign consent in their private area. Second, the online questionnaire will directly ask participants. Third, study participants can choose the location for blood sampling when making an appointment in the given time frame, i.e., police station versus Interregionale Blutspende SRK. In the latter location, privacy can be guaranteed, whereas in the former location, working colleagues will be aware of blood sampling, and hence, study participation.

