4 STATISTICS AND METHODOLOGY

4.1. Statistical analysis plan

We consulted a statistician from the CTU Bern ([name]), and we will conduct the study in collaboration with the department of statistics of the CTU Bern. In 2019, the police department of the canton of Bern listed 2'491 fulltime equivalents [24]. Nix et al. examined response rates to 497 police surveys reported in 390 articles published in 15 journals from 2008 to 2017, and found a mean response rate of 64.3% (St. Dev. 25.9) [27]. Because our survey includes serum sampling, we estimated a conservative voluntary study participation of 25% (i.e., approx. 625 individuals). We also performed a pre-study survey within the police department, and 927 individuals confirmed their interest to participate. Hence, this pre-study investigation corrects our sampling size estimate to 1'000 study participants.

For the primary endpoint, we hypothesize that the COVID-19 seroprevalence within the police department will be between 1% and 2% at the beginning of the study. We further hypothesize that the seroprevalence will increase during the study period by 8% (i.e., from 2% to 10%). A precision-based sample size calculation will be applied to reduce the margin of error.

Considering the uncertainty from the serological survey and including our validation results and

the manufacturer's data, we calculate a sensitivity of 97% and a specificity of ≥99% for detecting SARS-CoV-2 antibodies in serum [28].

Proportion, %	CI width (%) for				
	800 Participants	1000 Participants	1200 Participants	1400 Participants	1600 Participants
1%	15	13	12	11	10
2%	20	18	16	15	14
3%	24	21	20	18	17
4%	27	24	22	21	19
5%	30	27	25	23	21
6%	33	30	27	25	23
7%	36	32	29	27	25
8%	38	34	31	28	27
9%	40	36	32	30	28
10%	42	37	34	31	29

Reading example: Including 1200 participants yields a CI 13.4 to 29.6%, given a true proportion of 2%.

The Table demonstrates sample size consideration to derive the precision (width of 95% confidence interval, CI) for a specific seroprevalence achieved when the corresponding number of policemen of Kanton Bern is included into the prospective cohort study using serological testing. The Wilson method was used to calculate CIs.

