Appendix 2: The categorization of variables

Parameter	Definition	Source of data to calculate the parameters
Cumulative incidence	The proportion of individuals with seropositivity	Laboratory result
Age- and gender specific attack rate	The proportion of individuals per age and gender strata with seropositivity	Laboratory result Questionnaire
Symptomatic proportion of cases	The proportion of individuals with seropositivity who showed symptoms or signs of COVID-19 infection (+/- confirmed PCR result in the past)	Questionnaire
Asymptomatic proportion of cases	The proportion of individuals with seropositivity who showed no symptoms or signs of COVID-19	Questionnaire
Attack rate in risk group (health-related data) (Persons over 65 years are not included because retirement is expected at this age in the study population).	Study participants with one or more of the following risk factors: diabetes, arterial hypertension, cardiovascular disease, chronic pulmonary disease, immuno-compromised because of host diseases or because of medical treatment, cancer, obesity (BMI > 30 kg/m ²)	Laboratory result Questionnaire
Activity related cumulative incidence	The proportion of individuals with seropositivity in the following 2 groups: Group 1: Police officers with fieldwork activity and frequent population contact. Group 2: office and administration occupation with low population contact.	Laboratory result Questionnaire
Geography related cumulative incidence	The proportion of individuals with seropositivity in the following 2 groups: Group 1: occupation in cities (Bern, Thun, Biel) Group 2: occupation in rural area of Bern or in cities but not belonging to group 1.	Laboratory result Questionnaire
Sub-study in seropositive study participants		
Parameter	Definition	Source of data to calculate the parameters
Serological response to infection	The change in serum level of specific antibodies to COVID-19 virus (increase in antibody titres)	Laboratory result over time
Seropositive result confirmation (specificity)	Seropositive result at baseline or seroconversion during the study year that will be confirmed with two additional serum samples, two and four weeks after the positive antibody result.	Laboratory result
Work or social environment-related exposure	Study participants perception of possible COVID-19 exposure	Questionnaire

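### Repeat draws at 2 and 4 weeks cannot remove a false positive that persists in the person, and no confirmatory use is stated for the spike assay already run on every sample

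*Combined protocol and SAP*

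**What the plan says.** Section 3.3, in the paragraph on reducing bias, gives the rule for positives: serum sampling is to be "repeated 2 and 4 weeks after the first positive antibody test result to confirm seropositivity and to exclude false positive results". Appendix 2 repeats it as a sub-study parameter labelled as specificity, with a seropositive result to be "confirmed with two additional serum samples, two and four weeks after the positive antibody result".

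Section 3.3 also states: "On each sample two commercially available SARS-CoV-2 serological assays will be performed". The targets differ: "One test detects anti-nucleocapsid antibodies, while the other detects anti-spikeprotein antibodies". The reason given for adding the spike assay is vaccination: "It is important for both the investigator and the study participant to identify antibodies derived from vaccination".

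Two specificity figures matter here. Section 3.3 quotes the manufacturer ("the specificity is 99.81" percent, 95% CI 99.65 to 99.91). Section 4.1 uses a planning floor: "we calculate a sensitivity of 97% and a specificity of ≥99% for detecting SARS-CoV-2 antibodies in serum".

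Three further provisions bear on the point. Section 3.3 sends antibody-positive samples to a neutralisation assay at the end of the study. Section 4.1 adjusts seroprevalence at each visit for false-positive and false-negative rates. Section 4.1 also fits a mixed logistic model for risk factors, for which it describes no such adjustment.

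**The concern.** A repeat draw tests whether the first result was a laboratory or handling accident. It does not test whether the antibody detected was raised by SARS-CoV-2. If a false positive comes from a cross-reacting antibody that lasts a month, both repeat draws will be positive and the person will count as confirmed. A second antigen addresses that question more directly, and the result is already in the database.

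The plan does not say how seropositivity follows from the two results, which assay decides on the repeat samples, or how discordant or unconfirmed results are classified.

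At stake are the analyses that treat each positive person as infected: the field/office and city/rural odds ratios, the symptomatic proportion, and the titre and neutralisation trajectories. Non-cases counted as cases pull the odds ratios towards 1 and dilute the rest. The problem is greatest at baseline, where the plan expects 1% to 2% prevalence.

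**Working it through.** The plan gives no false-positive count or predictive value for its confirmation step, so there is no figure of its own to reproduce.

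**Inputs.** N = 1000, prevalence p = 1% to 2% rising to 10%, sensitivity (Se) 97% and specificity (Sp) of at least 99% (Section 4.1); Sp 99.81% (Section 3.3). Two quantities are not in the documents and are varied as assumptions: ρ, the share of false positives that persist in the person, and c, the chance that the second assay is also falsely positive when the first is. The second assay is given the same 97% sensitivity, also an assumption.

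**1. One assay, no confirmation.** True positives TP = N·p·Se; false positives FP = N·(1−p)·(1−Sp); PPV = TP/(TP+FP).

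| p | TP | FP, Sp 99% | PPV | FP, Sp 99.81% | PPV |
|---|---|---|---|---|---|
| 1% | 9.7 | 9.9 | 49.5% | 1.9 | 84% |
| 2% | 19.4 | 9.8 | 66.4% | 1.9 | 91% |
| 10% | 97.0 | 9.0 | 91.5% | 1.7 | 98% |

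**2. Repeat draws, all three samples positive.** FP remaining = FP·[ρ + (1−ρ)(1−Sp)²], taking true positives to stay positive. At p = 1%:
- ρ = 0 (purely random error): practically none remain, even at Sp 99%.
- ρ = 0.5: 4.95 remain at Sp 99% (PPV 66.2%) and 0.94 at Sp 99.81% (PPV 91.2%).
- ρ = 1: all remain, and PPV is as in step 1.

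**3. Both antigens positive on the index sample.** FP remaining = FP·c; TP = 1000 × 0.01 × 0.97 × 0.97 = 9.41 if misses are independent. At p = 1% and Sp 99%:
- c = 0.01 (independent errors): FP 0.099, PPV = 9.41/(9.41 + 0.099) = 99.0%.
- c = 0.10: FP 0.99, PPV 90.5%.
- c = 0.50: FP 4.95, PPV 65.5%.

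**4. Odds ratios.** The observed proportion in each group is Se·p + (1−Sp)(1−p). Take a true odds ratio of 2.0, two equal groups (assumption) and no false positives removed. At 1% average prevalence (1.33% against 0.67%):
- Sp 99%: 2.28% against 1.64%, observed odds ratio 1.40.
- Sp 99.81%: 1.48% against 0.84%, observed odds ratio 1.77.

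At 2% average prevalence the observed values are 1.57 and 1.87, and at 10% they are 1.87 and 1.97.

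**5. The Section 4.1 adjustment.** Adjusted prevalence = (crude + Sp − 1)/(Se + Sp − 1).
- Single-assay counts at Sp 99%, true prevalence 1%: (0.0196 − 0.01)/0.96 = 1.00%. The truth is recovered.
- Counts taken after half the false positives are removed, same single-assay figures: (0.01465 − 0.01)/0.96 = 0.48%. This over-corrects.

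**The case against.** The strongest defence is that the plan already protects its primary estimate. The adjustment for test error recovers prevalence in expectation if Se and Sp are known and match the way positives are counted. That stands, and it is why this point is not about the prevalence figure. It does not extend to classification of individuals.

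The size is also contestable. The large effects need the 99% floor. At the manufacturer's figure, PPV is 84% at 1% prevalence with no confirmation at all, and an odds ratio of 2.0 is seen as about 1.8. The model uses all five visits, and the plan expects prevalence to reach 10%. This stands too.

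Four stronger readings are tempting, and the documents do not support them:
- *The spike result is ignored.* It has a stated role in vaccination, and since both assays run on each sample, the repeat samples may carry both. What can be said is that no confirmatory use is stated.
- *The spike result is an independent check.* No error correlation is given, nor any separate spike performance. At c = 0.5 the two-antigen rule (65.5%) does no better than repeat draws with ρ = 0.5 (66.2%).
- *Cross-reactions normally persist.* That is plausible, but no persistence rate is given.
- *True infections that turn negative are discarded.* No section makes persistence a condition for any endpoint or removes an unconfirmed positive. Appendix 2 defines attack rates and the symptomatic proportion by seropositivity and lists confirmation only as a sub-study parameter.

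Finally, neutralisation testing of positives gives a further functional result on them. It comes at study end and has no stated confirmatory role, but it can be given one.

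**Conclusion.** The point holds as a cheap improvement to case definition, not as a flaw in the primary prevalence estimate. Repeat draws are named as the means of excluding false positives, and they cannot exclude those that persist in the person. At 1% prevalence the share of single-assay positives that are real lies between 49.5% and 84%, depending on which of the plan's own specificities applies; at 10% it lies between 91.5% and 98%. The consequence is mainly attenuation of the risk-factor odds ratios (2.0 seen as 1.4 to 1.8 at 1% prevalence, if no false positives are removed) and contamination of the symptomatic, titre and neutralisation analyses.

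How much a two-antigen rule gains over repeat draws rests on ρ and c, which are assumptions here. It is large if errors on the two assays are close to independent and vanishes if half of them coincide.

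**What to change.** In Section 3.3 (bias paragraph), Section 4.1 and Appendix 2:

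1. For participants unvaccinated at the index draw, define confirmed infection in the case-based and risk-factor analyses as nucleocapsid and spike both positive on that sample.
2. Resolve discordant results with the repeat draws, tested on both assays, and with the planned neutralisation result.
3. For vaccinated participants, where a positive spike result cannot confirm infection, label cases as nucleocapsid-only and report results with and without them.
4. Match the test-error adjustment to the rule used to count positives: single-assay Se and Sp for single-assay counts only; otherwise the Se and Sp of the combined rule, over a stated range of error correlation.
5. Reconcile the number of repeat draws. The bias paragraph and Appendix 2 give two. The earlier text of Section 3.3 and Figure 2 give one for unvaccinated positives.

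**Cost.** No new type of assay is needed. Index-sample sensitivity falls from 97% to about 94% (0.97 × 0.97 = 0.941) under independence, partly recovered by the repeat draws. The combined-rule adjustment needs joint performance figures that the documents do not give, hence the stated range. The neutralisation result arrives only at study end, so it can inform the final analysis but not the results sent to participants within 2 weeks.
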